**Schema**

Cycle length= 14 days

Generic name: Nasal Rose Geranium in Sesame Oil	Generic name: Nasal Isotonic Saline
Brand name(s): N/A	Brand name(s): N/A
Availability: Gateway Pharmacy	Availability: Gateway Pharmacy

## 1.0 Background

Dryness, crusting, pain, and bleeding of the nostrils due to inflammation, termed nasal vestibulitis, is infrequently reported in the literature as a side effect of cancer-directed therapy, but recent reports support that this is a common clinical problem for which patients desire an effective intervention. One retrospective study described 115 patients who developed nasal vestibulitis while undergoing targeted therapy (1). Recently, a Mayo study surveyed 100 patients, who had undergone at least 6 weeks of cancer-directed therapy, regarding the presence of nasal symptoms (2). Forty-one percent of the 100 surveyed patients reported nasal symptoms, including dryness, pain, bleeding, and scabbing. Higher frequencies were reported among those who had received taxanes (71%), and VEGF-related therapies (78%).

The current literature does not guide providers as to how best to treat nasal vestibulitis. Topical antibiotics may offer some benefit for nasal vestibulitis associated with cancer-directed therapy. Of the 115 patients undergoing targeted therapy and evaluated by Ruiz et al, 95% of patients were treated with topical or oral antibiotics by a dermatology provider, and 60% reported symptom resolution (1), but this has not been prospectively studied.

Another potential therapy for nasal vestibulitis is rose geranium in sesame oil nasal spray. This compound was initially evaluated in a small study, which showed that it decreased epistaxis severity among patients with hereditary hemorrhagic telangiectasia (2-4). After rose geranium in sesame oil nasal spray was anecdotally noted to improve nasal vestibulitis symptoms, a retrospective evaluation of its potential benefit in breast cancer patients undergoing cancer-directed therapy at Mayo Clinic was conducted. Of the 20 patients who used the nasal spray product and responded to surveys, all reported symptomatic benefit, and 8 (40%) reported dramatic or complete resolution of symptoms.

While very rare cases of lipid pneumonia have been reported after ingestions of large amounts of sesame oil, this compound was generally well tolerated; although two patients reported unpleasant effects: one commented that it was “messy” and another noted that it left an “oily coating at the back of the throat” (5, 6). A prospective study of rose geranium in sesame oil nasal spray is needed to better determine the potential benefit of this compound.

The current trial is designed to prospectively evaluate the utility of a rose geranium in sesame oil nasal spray for treating established nasal vestibulitis.

Nasal isotonic saline has not been studied in nasal vestibulitis. Limited data report that nasal isotonic saline mildly improves symptoms of rhinosinusitis, but it is most efficacious when utilized as a part of high-volume nasal irrigation (7-9). While it is frequently used to treat dry nasal passages, isotonic saline nasal spray was used as a placebo control in a trial evaluating a sesame oil nasal spray for weather-related dry nasal mucosa (4).

### 1.1 Treatment

#### 1.11. Dosing and scheduling of rose geranium in sesame oil nasal spray

This trial will be an evaluation of rose geranium in sesame oil nasal spray versus nasal saline. Rose geranium in sesame oil nasal spray is a compounded preparation, containing 0.2 mL (4 drops) of pharmaceutical grade rose geranium oil to 119.8 mL of pharmaceutical grade sesame oil and then put into 30mL bottles. This is the same compound that was used in the aforementioned study of patients with hereditary hemorrhagic telangiectasia (2). Isotonic nasal saline will contain 0.9% sodium chloride with benzalkonium chloride, as a preservative, in a 30 mL bottle.

#### 1.12 Treatment duration

The therapy will be given for two weeks. This should give us adequate time to determine whether rose geranium in sesame oil nasal spray can decrease nasal vestibulitis.

Following that two week period, participants taking the saline spray will be allowed to cross over to the other spray. Subjects may cross over within two weeks after completion of treatment and be on therapy for an additional two weeks such a patient must still be receiving chemotherapy or within 2 weeks of the last chemotherapy dose, at the time of crossover.

## 2.0 Goals

### 2.1 Primary Goal

To determine the ability of rose geranium in sesame oil nasal spray to alleviate nasal vestibulitis in patients undergoing systemic, antineoplastic therapy when compared with isotonic nasal saline.

### 2.2 Secondary Goals

To assess toxicities related to rose geranium in sesame oil nasal spray in this study situation.

## 3.0 Registration Patient Eligibility

### 3.1 Registration - Inclusion Criteria

- 3.11 Age  $\geq$ 18 years and be diagnosed with cancer and receiving chemotherapy
- 3.12 Ability to provide informed consent
- 3.13 Willingness to complete questionnaires
- 3.14 ECOG Performance Status (PS) 0, 1, 2
- 3.15 One or more of the following nasal symptoms for which the patient reports they would appreciate treatment. Symptoms must have started after the initiation of systemic, antineoplastic therapies, be attributed to the systemic, antineoplastic therapies, and symptoms must be reported as being moderate (corresponding to a score of 2) or worse on a scale from mild (1) to very severe (4) on at least one of the items below.
  - a. Dryness

- b. Discomfort/Pain
- c. Bleeding
- d. Scabbing
- e. Sores

3.2 **Registration - Exclusion Criteria**

- 3.21 Predisposition to epistaxis prior to the initiation of cancer-directed therapy (more than once a month over the previous year).
- 3.22 Planned initiation or continuation of any topical nasal treatment other than the studied nasal spray,(such as nasal steroids, Ayr nasal gel, Neosporin ointment or nasal administration of petroleum jelly). Taking Imitrex for migraines is acceptable.
- 3.23 Previous exposure to rose geranium in sesame oil nasal spray.
- 3.24 Concurrent upper respiratory tract infection
- 3.25 History of allergic or other adverse reactions to sesame oil or essential rose geranium oil
- 3.26 Any other reason that the study clinician or investigator feels precludes safe or appropriate inclusion in this study
- 3.27 Vulnerable populations: pregnant women, prisoners, mentally handicapped.

3.3 **Re-Registration:**

- 3.31 The patient will be un-blinded and determined to have been on the saline arm, when initially randomized.

#### 4.0 Test Schedule

Tests and procedures	Active Monitoring Phase		
	≤ 14 days prior to Registration	Baseline (Day 1)	Days 7 and 14
Window			±3 days
History and appropriate physical exam	X		
Adverse event assessment		X	X
Baseline pre-nasal spray questionnaire (App I)		X 	
Nasal symptom and patient experience questionnaire (App II). Nurse should ensure that this contains a record of patient's most prominent nasal symptom at baseline			X
Nurse/research staff call 			X

1. Phone evaluation once weekly, to remind patients to complete questionnaires and evaluate AEs.
2. Administer questionnaire on the same day nasal spray starts, making sure that the patient completes the questionnaire prior to receiving the study spray

Cross-Over Continuation Phase (For Initial Saline participants only)		
Tests and procedures	Baseline (Day 1)	Days 7 and 14 after cross-over
Window	±14 days	± 3 days
Patient contact (Nurse visit/call)	X	
Adverse event assessment		X
Baseline pre-nasal spray questionnaire (App I)	X 	
Nasal symptom and patient experience questionnaire (App II). Nurse/research staff should ensure that this contains a record of patient's most prominent nasal symptom at baseline		X
Nurse/research staff call 		X

1. Phone evaluation once weekly, to remind patients to complete questionnaires and evaluate AEs
2. Administer questionnaire on the same day nasal spray starts, making sure that the patient completes the questionnaire prior to receiving the study spray

#### 4.1 Survival Follow-up: N/A

## 5.0 Stratification Factors

5.1 **Gender:** Male vs. Female

5.2 **Age:** ≤ 50 vs. > 50

5.3 History of **Seasonal Allergies and/or Asthma:** Yes vs. No

## 6.0 Registration/Randomization Procedures

### 6.1 Registration Procedures

To register a patient, access the Registration Application at [registration.mayo.edu](http://registration.mayo.edu). The Registration Application is available 24 hours a day, 7 days a week. If unable to access the application, contact the Mayo Clinic Site Management Team ([[contact]](mailto:[contact]), [contact]) between the hours of 8am and 4:30pm Central Time, Monday through Friday.

Prior to initiation of protocol treatment, this process must be completed in its entirety and a MCCC Subject ID number (R#####) must be assigned. It is the responsibility of the individual registering the patient to confirm the process has been successfully completed prior to release of the study agent.

All Institutions:

### 6.2 Verification of materials

Prior to accepting the registration, registration/randomization application will verify the following:

- IRB approval at the registering institution
- Patient eligibility
- Existence of a signed consent form
- Existence of a signed authorization for use and disclosure of protected health information

### 6.3 Documentation of IRB approval

Documentation of IRB approval must be on file in the Registration Office before an investigator may register any patients.

In addition to submitting initial IRB approval documents, ongoing IRB approval documentation must be on file (no less than annually) at the Registration Office ([contact]). If the necessary documentation is not submitted in advance of attempting patient registration, the registration will not be accepted and the patient may not be enrolled in the protocol until the situation is resolved.

When the study has been permanently closed to patient enrollment, submission of annual IRB approvals to the Registration Office is no longer necessary.

### 6.4 Treatment start

Treatment cannot begin prior to registration and must begin ≤14 days after registration.

### 6.5 Baseline symptoms

Only nasal symptoms are required to be documented at baseline, within one day prior to starting the spray.

### 6.6 Study drug

Study agent will have been sent to the institution entering the patient.

#### 6.7 Patient questionnaire booklets

Patient questionnaire booklets are available on site. Copies are not acceptable for these submissions. Booklets should be ordered using the Patient Questionnaire Order Form

#### 6.8 Study Conduct

The clinical trial will be conducted in compliance with regulations (21 CFR 312, 50, and 56), guidelines for Good Clinical Practice (ICH Guidance E6), and in accordance with general ethical principles outlined in the Declaration of Helsinki; informed consent will be obtained from all participating patients; the protocol and any amendments will be subject to approval by the designated IRB prior to implementation, in accordance with 21 CFR 56.103(a); and subject records will be stored in a secure location and subject confidentiality will be maintained. The investigator will be thoroughly familiar with the appropriate use of the study drug. Essential clinical documents will be maintained to demonstrate the validity of the study and the integrity of the data collected. Master files should be established at the beginning of the study, maintained for the duration of the study and retained according to the appropriate regulations.

#### 6.9 Randomization Procedures

- 6.9a1 The factors defined in Section 5.0, together with the registering membership, will be used as stratification factors.
- 6.9a2 After the patient has been registered into the study, the values of the stratification factors will be recorded, and the patient will be assigned to one of the following treatment groups saline vs rose geranium in sesame oil using the Pocock and Simon dynamic allocation procedure which balances the marginal distributions of the stratification factors between the treatment groups (Pocock-Simon ref – see below).

#### Procedures for Double Blinding the Treatment Assignment

After the treatment assignment has been ascertained by the registration/randomization application, the patient's study medication code number will be displayed on the confirmation of registration screen.

MCCC Registration Office personnel will monitor the supply of coded bottles at each participating institution and will arrange for the research pharmacist to send further supplies to the participating institutions as needed.

#### 6.9b Crossover Registration (Step 2)

To register a patient, access the Registration Application at [registration.mayo.edu](http://registration.mayo.edu). The Registration Application is available 24 hours a day, 7 days a week. If unable to access the application, contact the Mayo Clinic Site Management Team ([[contact]](mailto:[contact]), [contact]) between the hours of 8am and 4:30pm Central Time, Monday through Friday.

Prior to initiation of protocol treatment, this process must be completed in its entirety.. It is the responsibility of the individual registering the patient to confirm the process has been successfully completed prior to release of the study agent.

- 6.9b3 Treatment cannot begin prior to registering to the crossover phase and will ideally begin ≤14 days after registration for the crossover phase.

## 7.0 Protocol Treatment

### 7.1 Treatment Schedule

#### 7.12 Treatment medication table

Arm	Agent	Dose Level	Route	Days	Cross-over continuation phase
A	Rose Geranium in Sesame Oil Nasal Spray	1 spray into each nostril twice daily. One additional spray can be administered if the first spray is not a full spray	Intranasal	1-14 twice daily	N/A
B	Nasal Saline	1 spray into each nostril twice daily. One additional spray can be administered if the first spray is not a full spray	Intranasal	1-14 twice daily	Administer the cross-over nasal preparation, in the same manner as the first randomization.

Participants should not be taking other topical nasal preparations at the same time as the provided nasal sprays. If the patient develops a concurrent infection or allergic episode involving the nasal passages (i.e. sinusitis or allergic rhinitis) after enrollment, the treating physician should provide the appropriate treatment for this infection.

### 7.2 Breaking Codes in Double-Blinded Studies

#### Emergency Unblinding Procedures

In the event of an emergency, call the MCCC Registration Office at [contact] to break the code on Monday through Friday, 8:00 a.m. to 4:30 p.m. Central Time. If the code must be broken after hours, assume the patient was assigned to active treatment and treat accordingly. Place a call to the MCCC Registration Office and leave a message informing them of the need to un-blind a patient. Provide your contact information so that MCCC Registration Office personnel can return the call the next business day.

#### Protocol-Specific Unblinding Procedures

Trial participants who complete initial protocol treatment may be unblinded. To unblind the patient, call the MCCC Registration Office [contact]) Monday through Friday, 8:00 a.m. to 4:30 p.m. Central Time to find out if the patient was receiving nasal rose geranium in sesame oil or nasal isotonic saline. Upon confirmation by the nurse/research staff call that all questionnaires have been completed and sent in the mail, the treatment assignment may be unblinded. Patients who were assigned nasal isotonic saline may proceed with the crossover phase and must be re-registered per the instructions in Section 6.9b.

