10.62 All other AEs

Submit via appropriate MCCC Case Report Forms (i.e., paper or electronic, as applicable) the following AEs experienced by a patient and not specified in Section 10.6:

10.621 Grade 1 and 2 AEs deemed *possibly, probably, or definitely* related to the study treatment or procedure.

10.622 Grade 3 and 4 AEs regardless of attribution to the study treatment or procedure.

10.623 Grade 5 AEs (Deaths)

10.6231 Any death within 30 days of the patient’s last study treatment or procedure regardless of attribution to the study treatment or procedure.

10.6232 Any death more than 30 days after the patient’s last study treatment or procedure that is felt to be at least possibly treatment related must also be submitted as a Grade 5 AE, with a CTCAE type and attribution assigned.

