The constellation of adverse events (AEs) as scored using the National Cancer Institute Common Terminology Criteria for Adverse Events, v5.0 (CTCAE v5.0) will be summarized within arms by reporting the number and percentage of patients. Specifically, to evaluate the AE profiles associated with each arm, the maximum grade for each type of AE will be recorded for each patient and frequency tables will be reviewed to determine overall patterns and compared between arms using Wilcoxon tests.

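### Section 7.2 lets a patient's arm be released before the Day 14 adverse events have been graded and attributed, leaving a small opening for bias in the between-arm comparison of low-grade AEs

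*Combined protocol and SAP*

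**What the plan says.** Section 7.2 (Protocol-Specific Unblinding Procedures) opens routine unblinding to both arms, patient by patient: "Trial participants who complete initial protocol treatment may be unblinded". The release condition is: "Upon confirmation by the nurse/research staff call that all questionnaires have been completed and sent in the mail, the treatment assignment may be unblinded". Saline patients may then cross over, and 3.31 makes unblinding part of re-registration.

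The Test Schedule (4.0) puts an AE assessment and a staff call at Days 7 and 14. Its footnote gives the purpose of the call: "Phone evaluation once weekly, to remind patients to complete questionnaires and evaluate AEs".

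Section 10.62 decides which AEs reach the case report forms. For low grades it lists "Grade 1 and 2 AEs deemed *possibly, probably, or definitely* related to the study treatment or procedure". For higher grades it lists "Grade 3 and 4 AEs regardless of attribution to the study treatment or procedure".

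Section 16.5 takes each patient's maximum grade for each type of AE, after which "frequency tables will be reviewed to determine overall patterns and compared between arms using Wilcoxon tests".

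**The concern.** The release rule protects the efficacy questionnaires but does not mention the AE record. For Grade 1-2 events, attribution is the entry filter: an event judged unlikely to be related need not be submitted. If that judgement is made or revised once the arm is known, the filter may differ between arms.

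The protocol also gives staff some reason to judge differently. Section 15.1 lists lipoid pneumonia, eye irritation, bad taste, and rash or burning for rose geranium. Section 15.2 lists no toxicity for saline.

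Toxicity of rose geranium is the only secondary goal (2.2), and the Wilcoxon comparison of AE grades is the only between-arm test planned for it. Differential attribution could create an apparent difference or hide a real one, depending on what staff expect. Low-grade events that were never submitted cannot be restored to the comparison later.

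**Working it through.** **1. What must precede release of the code**

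| Item | Required before release? | Where |
|---|---|---|
| Initial treatment complete | Yes | 7.2 |
| Questionnaires completed and mailed | Yes | 7.2 |
| AEs asked about on the weekly call | Scheduled, but not a release condition | 4.0, footnote 1 |
| AE grade and attribution recorded | Not stated | none found |
| Separate blinded AE assessor | Not stated | none found |

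**2. Which events are exposed**

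- Grade 3-4: submitted whatever the attribution (10.622), so their capture is not exposed.
- Grade 2 reported during dosing: Section 8.0 requires attributed Grade 2 or higher events to be recorded and acted on while the patient is on the spray, so the judgement precedes routine unblinding.
- What remains: Grade 1 events, and Grade 2 events first reported at the Day 14 contact.

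**3. Size under assumed rates**

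The plan gives no AE rate and no operating characteristic for this test, so there is no stated figure to reproduce. Its only power figure, 85% for the primary endpoint, does not enter.

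Input from the plan: 53 per arm (16.3). Assumptions:
- no true difference between arms;
- weekly event probability p, with Grade 1 and Grade 2 split 70/30;
- blinded attribution 40% in both arms;
- Week 2 attribution after unblinding of 40% + d (rose geranium) and 40% − d (saline);
- only attributed events recorded, and maximum grade compared by two-sided Wilcoxon at 5%.

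Probability that a patient has a recorded event, with all Week 2 attributions unblinded:

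1 − (1 − 0.4p)(1 − (0.4 ± d)p)

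- p = 0.4, d = 0.2: 1 − 0.84 × 0.76 = 36.2% against 1 − 0.84 × 0.92 = 22.7%
- p = 0.2, d = 0.2: 1 − 0.92 × 0.88 = 19.0% against 1 − 0.92 × 0.96 = 11.7%
- p = 0.1, d = 0.2: 1 − 0.96 × 0.94 = 9.8% against 1 − 0.96 × 0.98 = 5.9%

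False-positive rate by simulation (4,000 trials per cell), all Week 2 attributions unblinded:

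| Weekly p | d = 0 | d = 0.1 | d = 0.2 |
|---|---|---|---|
| 2% | 0.8% | 1.3% | 1.4% |
| 5% | 4.2% | 5.1% | 6.6% |
| 10% | 4.6% | 5.8% | 10.8% |
| 20% | 4.4% | 7.4% | 16.9% |
| 40% | 4.6% | 11.6% | 32.0% |

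The simulation standard error is √(0.05 × 0.95/4000) = 0.3 points near 5%, and √(0.32 × 0.68/4000) = 0.7 points at 32%.

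With half the Week 2 attributions unblinded:
- p up to 10%: no more than about 6%, even at d = 0.2;
- p = 20%: 5.2% (d = 0.1) and 7.2% (d = 0.2);
- p = 40%: 7.0% and 11.1%.

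Section 16.5 tests each AE type separately. The rows from 2% to 10% are meant to represent single types, and those at 20% and 40% are closer to all AEs pooled, which the plan does not test.

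**4. Sensitivity to the assumed shift**

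A simpler exact calculation treats the event as recorded or not, with 53 per arm, 50% blinded attribution, half the events attributed after unblinding, and true AE rates of 20-60%. Unblinded attribution of 60% against 40% gives 6-10%. At 75% against 25% it gives 13-39%. In the last case with a 60% true rate, the recorded proportions are 0.6 × (0.25 + 0.375) = 37.5% and 0.6 × (0.25 + 0.125) = 22.5%. The result follows the assumed shift, about which the documents say nothing.

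**The case against.** The strongest reply is that the schedule already handles this. The call that confirms the questionnaires is the call on which AEs are evaluated, so the Day 14 AE account should normally exist before anyone asks for the code. No section describes attribution being put off until afterwards. This stands as far as taking the history goes. It does not cover recording the grade and attribution, or changing them later, and those steps decide whether a Grade 1-2 event is submitted.

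A second reply also stands in part. Question 12 of Appendix II asks about unpleasant effects on the same questionnaires that must be finished before release. That is a blinded tolerability record in both arms, and Day 7 AEs give a further blinded comparator. The bias would therefore not be wholly invisible. But Question 12 carries no CTCAE grade or attribution and does not feed the 16.5 test.

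A reader might infer more than the documents support:

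- **That half of all attributions are unblinded**, because Days 8-14 are 7 of 14 dosing days. Section 7.2 only permits unblinding, and only after treatment. The share of dosing days is not the share of attributions made with the arm known.
- **That a false-positive rate of 17-32% is to be expected.** In the main model this needs an event at 20-40% per week, every Week 2 attribution unblinded, and opposite 20-point shifts in the two arms. The documents supply none of these.
- **That efficacy is compromised.** The questionnaire holding the primary endpoint must be completed before release.

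**Conclusion.** The gap in 7.2 is real but minor. Nothing requires Day 14 grade and attribution to be fixed before the arm is known, and attribution filters the Grade 1-2 AEs that 16.5 compares.

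The size cannot be derived from the documents. For single AE types at 10% per week or less, the assumed scenarios stay near or below nominal with a 10-point shift in each arm (at most 5.8%). They reach 10.8% only with a 20-point shift and every Week 2 attribution unblinded. With half of Week 2 unblinded, the same types stay at or below about 6%. The main model reaches about 32% only for a pooled AE at 40% per week with all Week 2 attributions unblinded and 20-point shifts. Larger assumed shifts would give larger figures, without support in the plan.

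These figures show that the mechanism can matter, not that it will. The point is worth making because prevention is nearly free and unsubmitted events cannot be recovered.

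**What to change.** **Section 7.2.** Extend the release condition along these lines: *and the Day 14 AE assessment (term, grade and attribution) has been recorded before the assignment is released.* Emergency unblinding is unchanged.

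**Section 16.5.** Keep all AEs of the randomised phase in the main comparison. Flag those recorded or re-attributed after unblinding, and repeat the comparison without the flagged Grade 1-2 events as a sensitivity analysis. Late or re-attributed events should not be dropped from the main comparison. That would also remove Grade 3-4 events whose capture never depended on attribution. The sensitivity analysis cannot bring back events that were never submitted, so the change to 7.2 does most of the work.

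**Cost.** A short addition to each section, a check by the Registration Office before it releases a code, and a way of telling which AE entries came after release. Crossover may wait about a day, within the two-week window in 1.12. The sample size (80 evaluable, 106 in total), significance level and power are unchanged.
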